10.2.3.1 Summaries

The summaries for solicited AEs will be:

- The number and percentage of subjects with solicited local and systemic reactions during the first 30 minutes after each dose of trial vaccine, overall and by severity.

- The number and percentage of subjects with solicited local and systemic reactions during the first 7 days (including day of administration) after each dose of trial vaccine, overall and by severity (Summaries will be for the time periods of 1-7, 1-3 and 4-7 days after trial vaccine)
- Daily summary of the number and percentage of subjects with solicited local and systemic reactions during the first 7 days (including day of administration) after each dose of trial vaccine overall and by severity
- Summary of the day of first onset of each solicited AE
- Summary of the number of days with each solicited AE within 7 days after each trial vaccination

A horizontal stacked bar plot showing the percentage of participants with each solicited AE, any solicited AE, any solicited injection site reactions, and any solicited systemic AEs after dose 1 and dose 2 will be presented. This plot will break down the percentages by maximum severity, with the percentage of mild, moderate and severe events stacked for each solicited AE.

All solicited AEs will also be listed.

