10.1.2 Solicited Adverse Events

The occurrence of selected indicators of safety will be measured/collected for 7 days (including day of administration) following administration of each trial vaccine dose (including the day of administration) and will be recorded on the local and systemic AE CRF page as applicable and as listed in Table 10.1.

Any solicited local (in the RIGHT thigh) or systemic reactions observed as continuing beyond 7 days (including day of administration) following each trial vaccine dose will be recorded as an AE on the AE CRF for follow-up. For these persistent/prolonged solicited reactions the end date will be captured on the AE CRF to permit a separate analysis from the unsolicited AEs (see Section 10.4.2).

Table 10.1 Solicited Local (Injection Site) and Systemic Reactions

Solicited local (injection site) reactions:	Pain Erythema Induration Swelling
Systemic adverse events:	Drowsiness Irritability/fussiness Loss of appetite Fever* Vomiting Diarrhea

Body temperature will be collected and recorded. *Fever is defined as body temperature greater than or equal to 38°C (100.4°F) regardless of method used [16].

The severity of solicited safety parameters will be assessed as described in Table 10.2.

Table 10.2 Solicited Safety Parameters

Adverse Event	Severity Grade	Intensity
Pain at injection site	0	None
	1	Mild: Minor reaction to touch
	2	Moderate: Cries/protests on touch
	3	Severe: Cries when limb is moved/spontaneously painful
Erythema at injection site ^(a)	0	≤ 10 mm
	1	Mild: $>10 - \leq 20$ mm
	2	Moderate: $>20 - \leq 40$ mm
	3	Severe: >40 mm
Induration at injection site ^(a)	0	≤ 10 mm
	1	Mild: $>10 - \leq 20$ mm
	2	Moderate: $>20 - \leq 40$ mm
	3	Severe: >40 mm
Swelling at injection site ^(a)	0	≤ 10 mm
	1	Mild: $>10 - \leq 20$ mm
	2	Moderate: $>20 - \leq 40$ mm
	3	Severe: >40 mm
Drowsiness	0	Behavior as usual
	1	Mild: Drowsiness easily tolerated
	2	Moderate: Drowsiness that interferes with normal activity
	3	Severe: Drowsiness that prevents normal activity
Irritability/fussiness	0	Behavior as usual
	1	Mild: Crying more than usual/no effect on normal activity
	2	Moderate: Crying more than usual/interferes with normal activity
	3	Severe: Crying that cannot be comforted/prevents normal activity
Loss of appetite	0	Appetite as usual
	1	Mild: Eating less than usual/no effect on normal activity
	2	Moderate: Eating less than usual/interferes with normal activity
	3	Severe: Not eating at all
Vomiting	0	None

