10.4.2 Collection and Reporting of Solicited Reactions

The occurrence of selected indicators of safety will be collected on the eDiary by the subject's LAR for 7 days (including day of administration) after administration of each dose of trial vaccine (including the day of administration, corresponding to Visit 2 (when the subject is 4 months of age) for Dose 1 and Visit 3 (when the subject is 6 months of age) for Dose 2 and will be recorded on the local and systemic AEs eCRF, as applicable. These will be summarized in the final CSR under the category solicited reactions to differentiate them from unsolicited AEs. Any solicited local or systemic reaction observed as continuing beyond 7 days after any trial vaccine administration will be recorded as an AE on the AE eCRF for follow-up.

Any solicited reaction that meets any of the following criteria must be entered as an AE on the AE eCRF page.

- Solicited local or systemic reactions that lead the subject to withdraw from the trial or further dose.
- Solicited local or systemic reactions that lead to the subject being withdrawn from the trial or further dose by the investigator.

Solicited local and systemic reactions that otherwise meet the definition of an SAE (see Section 10.1.5).

10.4.3 Collection and Reporting of Adverse Events of Special Interest/ Medically-Attended Adverse Events

AESIs will not be collected.

MAAEs will be collected by close monitoring throughout the trial. MAAEs must be recorded as an AE on the AE eCRF page.

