13.1.3 Safety Analysis

All safety summaries will be provided for each trial arm and overall.

Solicited reactions:

Solicited reactions will be assessed 30 minutes after administration of each dose of trial vaccine, and then daily for 7 days (including the day of administration). For each solicited reaction, the number and percentage of subjects who experienced an event will be computed, for each day from Day 1 to Day 7 post-dose (including the day of dose) and overall.

Solicited reactions will be summarized by severity. For subjects with more than 1 episode of the same event within an interval, the maximum severity will be used for tabulations.

Body temperature measurements will be summarized in categories (including fever, defined as temperature $\geq 38^{\circ}\text{C}$), without adjustment for the route of measurement. Summaries of the day of first onset of each event and the number of days subjects experienced each event will also be provided.

Data from the 30 minutes assessment of solicited reactions immediately post-vaccination will be summarized separately.

Unsolicited AEs:

Any unsolicited AEs, SAEs, MAAEs, and AEs leading to trial vaccine, routine vaccine or trial withdrawal, will be coded using MedDRA, and summarized by system organ class (SOC) and preferred term (PT) using number and percentage of subjects with an AE. Subjects with more than one occurrence for the term will be counted only once for this term. Unsolicited AEs will be collected up to 28 days after administration of each dose of trial vaccine and routine vaccine (including the day of administration); summaries will also be provided by event severity (mild, moderate, severe) and relationship (not related, related) to trial vaccine, routine vaccine or trial procedures. For subjects with more than one AE within an SOC or a PT, the AE with the maximum severity or strongest relationship within each SOC and each PT will be included in the summaries by severity or relationship, respectively.

Any unsolicited AEs will be summarized in the following 3 time intervals: 1) overall up to 28 days after each dose (including the day of administration), 2) with onset between 1 and 7 days after each dose (including the day of administration), and 3) with onset between 8 and 28 days after dose (including the day of administration).

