10.2.3 Solicited Adverse Events

The solicited safety parameters for this study are the injection site reactions of pain, erythema, induration and swelling and the systemic adverse events of drowsiness, irritability/fussiness, loss of appetite, fever (defined as body temperature greater than or equal to 38°C), vomiting and diarrhea.

Solicited reactions will be assessed 30 minutes after administration of each dose of trial vaccine, and then daily for 7 days (including the day of administration).

Body temperature measurements will be summarized in categories (including fever, defined as temperature $\geq 38^{\circ}\text{C}$), without adjustment for the route of measurement. Summaries of the day of first onset of each event and the maximum number of continuous days subjects experienced each event will also be provided.

Any solicited local or systemic reactions observed as continuing beyond 7 days following each trial vaccine dose will be recorded as an AE in the CRF.

Solicited AEs collected daily are entered in diaries by the participants Legally Acceptable Representative (LAR). The site investigator or designee will review the eDiary entries with the LAR and any data deemed to be implausible or incorrect may be updated during this review. The TFLs describe below will use the data entered by the LAR.

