10.2.4.1 Summaries

The summaries for unsolicited AEs will be:

- Overall Overview of the occurrence of all AEs.
- The number and percentage of subjects with any unsolicited AE during the first 28 days (including day of administration) after each dose of trial vaccine overall.
- The number and percentage of subjects with any unsolicited AE during the first 28 days (including day of administration) after each dose of trial vaccine by severity.
- The number and percentage of subjects with any unsolicited AE during the first 28 days (including day of administration) after each dose of trial vaccine by relationship to trial vaccine.
- The number and percentage of subjects with any unsolicited AE during the first 28 days (including day of administration) after each dose of trial vaccine by relationship to trial procedure.

Listings will be presented for all unsolicited AEs.

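### The SAP gives two different duration measures for solicited reactions, and none of its summaries uses the end date collected for reactions lasting beyond day 7

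*SAP*

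**What the plan says.** **Duration.** Protocol 13.1.3 states: "Summaries of the day of first onset of each event and the number of days subjects experienced each event will also be provided". In the matching sentence of SAP 10.2.3 the second item becomes "the maximum number of continuous days subjects experienced each event will also be provided". The list of outputs in SAP 10.2.3.1 then has a "Summary of the number of days with each solicited AE within 7 days after each trial vaccination". SAP section 13 lists two changes from the protocol, the hepatitis B assay and the strategy for schedule non-compliance. A change of duration measure is not among them.

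**Reactions beyond day 7.** Protocol 10.1.2 sends a solicited reaction still present after day 7 to the AE page and adds: "For these persistent/prolonged solicited reactions the end date will be captured on the AE CRF to permit a separate analysis from the unsolicited AEs". Protocol 10.4.2 says of the diary-collected reactions: "These will be summarized in the final CSR under the category solicited reactions to differentiate them from unsolicited AEs". SAP 10.2.3 says only that a reaction "continuing beyond 7 days following each trial vaccine dose will be recorded as an AE in the CRF". It also says the solicited outputs use the diary entries made by the infant's representative.

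**Unsolicited tables.** One SAP 10.2.4.1 table counts "subjects with any unsolicited AE during the first 28 days (including day of administration) after each dose of trial vaccine overall". SAP 10.2.4 limits the summaries to events after the first trial vaccine dose. Neither section says how an AE-page record that continues a solicited reaction is to be treated.

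**The concern.** Two sections of the SAP, one introducing the other, give the programmer different instructions for the same output. One of them also departs from the protocol without being declared.

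Separately, the protocol collects a date for a stated analytic purpose and the SAP does not take it up. How often a local or systemic reaction outlasts the diary week, and for how long, is part of the safety profile, and comparing that profile between arms is the safety objective (Protocol 5.1.3). HIL-214 contains 500 µg of aluminum as aluminum hydroxide and the placebo is saline (Protocol 8.1.1 and 8.1.2), so a difference between arms in prolonged local reactions is plausible, although the documents give no rate.

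The missing exclusion rule matters because Protocol 10.2 treats solicited reactions as related to trial vaccine by default. If such records entered the unsolicited tables, they would weigh most on the related-AE table, where the background rate is likely to be lower.

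**Working it through.** The plan states no figure for this point, so there is nothing to reproduce. The check compares the texts, applies the duration rules to example day patterns, and sizes the possible leakage under assumed rates.

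**1. Duration rules on example patterns (assumed; day 1 is the day of vaccination).** SAP 10.2.3.1 counts days with the reaction among days 1 to 7. SAP 10.2.3 takes the longest unbroken run; because its source is the 7-day diary, that run is also confined to days 1 to 7.

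| Days with reaction | Days within 7 (SAP 10.2.3.1) | Longest run in diary (SAP 10.2.3) | All days with reaction |
|---|---|---|---|
| 2–4 | 3 | 3 | 3 |
| 1, 2, 4, 5 | 4 | 2 | 4 |
| 1, 3, 5, 7 | 4 | 1 | 4 |
| 1–2, 4–5, 7–9 | 5 | 2 | 7 |
| 1–10 | 7 | 7 | 10 |
| 5–12 | 3 (days 5, 6, 7) | 3 | 8 (12 − 5 + 1) |

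The two SAP measures agree for unbroken reactions and part for intermittent ones. Neither shows a reaction's length past day 7.

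Protocol 13.1.3 sets no explicit cap, but the same section describes daily assessment for 7 days. Its number of days therefore reads most naturally as the SAP 10.2.3.1 count. In substance there are two measures, and the longest run in SAP 10.2.3 is the odd one out.

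**2. Where the end date goes.** Each solicited summary in SAP 10.2.3.1 that names a period covers the first 30 minutes or days within 1 to 7, and all use diary data. The end date sits on the AE page, so it enters none of them. SAP 7.5.2 imputes partial AE dates partly to calculate duration, but no table of AE duration is specified. Listings remain, and they give no rate or duration by arm.

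**3. Leakage, if it occurred.** Let *u* be an unsolicited AE rate common to both arms, and *a* and *b* the proportions with a prolonged solicited reaction on HIL-214 and placebo. If the two kinds of event are independent, the reported rate becomes 1 − (1 − *u*)(1 − *a*) on HIL-214, and likewise with *b* on placebo. The spurious difference is (1 − *u*)(*a* − *b*). All rates below are assumptions.

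| *a* v *b* | Any unsolicited AE, *u* = 30% | Related AE, *u* = 2% |
|---|---|---|
| 1% v 0.5% | 0.70 × 0.5 = 0.35 points | 0.98 × 0.5 = 0.49 points |
| 3% v 1% | 0.70 × 2 = 1.40 points | 0.98 × 2 = 1.96 points |
| 5% v 2% | 0.70 × 3 = 2.10 points | 0.98 × 3 = 2.94 points |

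With 200 infants per arm, the related-AE table would gain 200 × 0.98 × *a*, or about 2 to 10 infants on HIL-214, and 200 × 0.98 × *b*, or about 1 to 4 on placebo.

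**The case against.** The strongest reply is that most of this is silence, not error.

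- **Double counting.** A reader might infer that the same infant will be counted under both a solicited reaction and an unsolicited AE with onset in days 1 to 7. The documents do not support that. SAP 10.2.3 calls the record an AE, not an unsolicited AE. SAP 10.2.4 distinguishes unsolicited AEs, which are summarised, from all AEs, which are listed. The SAP assumes familiarity with a protocol that intends separation. Nor does any section say whether the AE-page start date is the true onset or the day after the diary ends. What stands is that the exclusion rule is not written down.
- **Three definitions.** A reader might count three duration definitions in the SAP. It has two, and the protocol's wording can be read as one of them. The conflict between SAP 10.2.3 and 10.2.3.1 stands.
- **The day-7 limit.** The solicited endpoint covers 7 days, the duration output is labelled as such, and 3 days is the correct entry for days 5 to 12 under that label. The daily summary also shows who still has a reaction on day 7. This is fair: the limit is not a mistake in that table. The gap is that nothing beside it reports what happened afterwards.
- **Obligation.** Protocol 10.1.2 permits a separate analysis and does not require one, and it alone gives that purpose; Protocol 10.4.2 sends continuing reactions to the AE page only for follow-up. So the SAP breaches no requirement, but it leaves unused a date collected for this purpose.
- **Consequence.** The trial is descriptive, and no test or decision rule depends on these tables. That limits the weight of the point.

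**Conclusion.** The point holds in three parts of unequal strength.

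1. SAP 10.2.3 and 10.2.3.1 conflict on duration. The longest-run measure also departs from Protocol 13.1.3 and is not declared in SAP section 13. This rests on the text alone. In the examples the gap is 2 to 3 days for intermittent reactions and nil for unbroken ones.
2. No SAP summary uses the end date of a prolonged reaction, so neither the rate nor the duration of such reactions will be reported by arm. This follows from the diary data source and the 7-day periods. How many infants are affected cannot be known from the documents.
3. The SAP has no explicit rule keeping these records out of the unsolicited tables. This is missing detail, not a planned miscount. The range of 0.35 to 2.94 percentage points illustrates what leakage could do under assumed rates and independence; it does not predict that it will happen.

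The change is worth making because it alters what is reported on the safety objective at little cost.

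**What to change.** - **SAP 10.2.3:** replace the longest-run wording with the number of days with the reaction in days 1 to 7, in line with Protocol 13.1.3 and SAP 10.2.3.1.
- **SAP 10.2.3.1:** add one table, by arm and dose, of the number and percentage of subjects with each solicited reaction ongoing after day 7, with the time from onset to the recorded AE-page end date. State which onset date is used. Keep this apart from the diary-day count: days with a reaction and elapsed calendar days are different quantities and should not be added together.
- **SAP 10.2.4:** state that AE-page records continuing a solicited reaction are flagged and left out of the unsolicited AE summaries, but stay in the SAE, MAAE and withdrawal tables where they qualify. This proviso is needed because Protocol 10.4.2 sends serious and withdrawal-related solicited reactions to the same page, and Protocol 13.1.3 places SAEs, MAAEs and withdrawal AEs under its unsolicited heading.

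The cost is SAP wording, one flag and one extra table. The end date is already collected. The AE fields listed in Protocol 10.4.1 include no link to a solicited reaction, so the flag may need matching on term and date at the blinded data review.

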10.2.4 Unsolicited Adverse Events

Unsolicited AEs will be collected up to 28 days after administration of each dose of trial vaccine (including the day of administration). Only unsolicited AEs recorded after the first dose of trial vaccine will be summarised. All AEs will be listed with the timing relative to the first dose indicated.

Any unsolicited AE will be summarized in the following 3 time intervals after each trial vaccine dose visit (Visit 2 and Visit 3):

- 1) Overall up to 28 days after each dose (including the day of administration)
- 2) With onset between 1 and 7 days after each dose (including the day of administration)
- 3) With onset between 8 and 28 days after dose (including the day of administration)

10.2.4.1 Summaries

The summaries for unsolicited AEs will be:

- Overall Overview of the occurrence of all AEs.
- The number and percentage of subjects with any unsolicited AE during the first 28 days (including day of administration) after each dose of trial vaccine overall.
- The number and percentage of subjects with any unsolicited AE during the first 28 days (including day of administration) after each dose of trial vaccine by severity.
- The number and percentage of subjects with any unsolicited AE during the first 28 days (including day of administration) after each dose of trial vaccine by relationship to trial vaccine.
- The number and percentage of subjects with any unsolicited AE during the first 28 days (including day of administration) after each dose of trial vaccine by relationship to trial procedure.

Listings will be presented for all unsolicited AEs.

10.2.5 Serious Adverse Events

10.2.5.1 Summaries

The summaries for SAEs will be:

- The number and percentage of subjects with SAEs during the corresponding collection periods overall
- The number and percentage of subjects with SAEs during the corresponding collection periods by severity
- The number and percentage of subjects with SAEs during the corresponding collection periods by relationship to trial vaccine.
- The number and percentage of subjects with SAEs during the corresponding collection periods by relationship to trial procedure.

All SAEs will be listed.

10.2.6 Medically Attended Adverse Events

Medically Attended Adverse Events (MAAEs) are defined as AEs leading to an unscheduled visit to or by a healthcare professional including visits to an emergency department, but not fulfilling seriousness criteria.

10.2.6.1 Summaries

The summaries for MAAEs will be:

- The number and percentage of subjects with MAAEs during the corresponding collection periods overall
- The number and percentage of subjects with MAAEs during the corresponding collection periods by severity
- The number and percentage of subjects with MAAEs during the corresponding collection periods by relationship to trial vaccine.
- The number and percentage of subjects with MAAEs during the corresponding collection periods by relationship to trial procedure.

All MAAEs will be listed.

10.2.7 Adverse Events Leading to Vaccine or Trial Withdrawal

10.2.7.1 Summaries

The summaries for AEs leading to vaccine or trial withdrawal will be:

- The number and percentage of subjects with AEs leading to vaccine or trial withdrawal, during the corresponding collection periods leading to vaccine or trial withdrawal overall.
- The number and percentage of subjects with AEs leading to vaccine or trial withdrawal, during the corresponding collection periods leading to vaccine or trial withdrawal by severity.

- The number and percentage of subjects with AEs leading to vaccine or trial withdrawal, during the corresponding collection periods leading to vaccine or trial withdrawal by relationship to trial vaccination.

All AEs leading to vaccine or trial withdrawal will be summarised and listed.

10.2.8 Deaths

All AEs that lead to death will be listed by vaccine group.

10.3 Extent of Exposure

All study drug administration details (including date and time, location of administration, and reason for no administration if applicable) will be listed.

The total number of doses each subject received of each childhood vaccination and HIL-214 will be summarised by counts and percentages. The time between doses will also be summarized.

The number and percentage of subjects who fulfil any of the criteria for delay of vaccination will be summarised at each visit along with the criteria that was satisfied.

10.4 Clinical Laboratory Evaluations

There will be no laboratory data collected other than the data needed for the immunogenicity analysis.

10.5 Vital Signs

The vital signs of heart rate and temperature will be summarised descriptively by visit.

Both vital signs parameters will also be listed.

